Furthermore, in response to the outbreak of COVID-19 these samples will be used to look for changes in seropositivity to SARS-CoV-2 in England children +/- young adults through 2020/2021 (and beyond if necessary) as a marker of infection with this novel coronavirus. This is to support Public Health England in its SARS-CoV-2 seroprevalence work, with a goal of providing blood samples from 400 participants per month through 2020 as a repeat cross-sectional seroprevalence study. While the majority of participants will provide a single blood sample, a subset of participants will be enrolled into a longitudinal sampling cohort, providing up to a total of 4 blood samples (and 3 saliva samples) allowing analysis of the kinetics of rise and fall of SARS-CoV-2 specific antibody concentrations following SARS-CoV-2 infection, and the relationship between serum and saliva antibodies. This will in turn inform the interpretation of data from the repeat cross-sectional seroprevalence study. The 'repeat' blood samples collected as part of this study will be counted towards the study target of blood samples from a sub-set of participants. The longitudinal sampling cohort will comprise of both seropositive and seronegative participants.

The longitudinal cohort also provides an opportunity to address the knowledge gap regarding T cell responses to SARS-CoV-2 infections. At present, it is not clear how many people who are infected do not mount an antibody response and whether they have a detectable T cell response only. Commentary in the literature suggests that measuring antibody levels alone may underestimate population level immunity against COVID-19 (Sekine et al., 2020). The longitudinal cohort provides an opportunity to examine both T cell responses and the kinetics of this response.

There will be enhanced recruitment in Black, Asian and Minority ethnic (BAME) populations to develop an understanding on whether higher rates of disease in the BAME community are a result of

- o Greater exposure to COVID-19 contacts
- A higher likelihood of being infected once exposed
- o Greater risk of disease once infection occurs

Previous seroprevalence studies

Seroprevalence studies using residual sera

PHE has been utilising residual serum samples from participating laboratories across the country as part of its ongoing seroprevalence programme for many years. These samples are used as a serum bank for

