investigating population immunity to a range of infections including vaccine preventable infections. These samples have been previously used to assess the population immunity for diphtheria with the last study undertaken using samples collected in 2009 ((Wagner et al.; Wagner et al., 2012), Box 1), whilst a number of seroprevalence studies have been undertaken at different times to study Men C population immunity. The most recent sampling was undertaken in 2014 (Box 2) when the teenage MCC vaccination programme was newly introduced.

Box 1. Wagner et al (2012) Immunity to tetanus and diphtheria in the UK in 2009

In this study, 150 residual sera were tested in each age group, in order to estimate the proportion of the population protected to within \pm 8% with 95% confidence. It found that:

- 75% of the UK population had antitoxin levels ≥0.01IU/mL correlating to basic diphtheria protection
- 41% had antitoxin levels ≥0. 1IU/mL correlating to full diphtheria protection
- Between ages 1 and 9 years, the proportion with antitoxin levels correlating to full protection remained stable (65%-71%)
- Thereafter, the proportion with antitoxin levels correlating to full protection declined to a low of 44% amongst those aged 10-11 years.
- The proportion with antitoxin levels ≥0.01IY/mL increased again for teenagers and young adults, before declining in older adults.
- The highest number of susceptibles with antitoxin levels < 0.01IU/mL were observed in the age groups <1 year (37%), 35-44 years (27%), 45-69 years (41%) and 70+ years (33%).

[figure not shown]

Figure 1: Diphtheria antitoxin distribution by age group in England, 2009. Error bars indicate 95% confidence intervals for full protection (Fig 5 from Wagner et al. (2012))

[figure not shown]

Figure 2. Seroprotection against serogroup C meningococci measured by proportions with serum bactericidal antibody (SBA) titres of \geq 8. Comparison of levels in 2014 with the previous surveys conducted prior to MCC vaccine introduction in 1996-1999 and following introduction in 2000-2004 and 2009 (Findlow et al., 2019)

Disadvantages of residual seroprevalence studies

- 1. Samples may not be representative of the whole population. Previous review of the source of these samples have shown considerable variation by age e.g. paediatric samples from immunocompromised children and samples for adults sourced from those attending Genito-Urinary Medicine clinics.

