7.8. Comparison with Residual Serum Samples

Data collected in this study will be compared with that obtained in the anonymised residual serum samples collected in 2019 from individuals aged 0 - 24 years by the PHE seroepidemiology unit from participating laboratories across England. These will be used as the basis of comparisons between immune responses measured through residual sample testing and through the active sample collection outlined in this protocol. The age, sex and year of collection will be known via a unique identity number: immunisation status will not be known.

In 2017, 3290 samples were collected in individuals aged 0 - 24. It is envisaged that a similar sample size will be collected in 2019/20, and that testing of the residual sera can take place in 2021.

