- For prospectively collected samples where vaccination history is known, in individuals aged 12 -24 years, the proportion of individuals within each age band that have serum bactericidal titres of ≥8 to group C meningococcal disease, and whether SBA titres are associated with adolescent Men ACWY or MCC vaccine or not having received vaccine. Trends by age and differences by vaccination status will be assessed by Chi-squared of Fisher's exact test as well as by using logistic regression. Comparisons by geometric mean titres will also be done by t-tests or Kruskal Wallis as appropriate and by plotting geometric means with 95% confidence intervals by age groups.
- Across the whole age range (0-24 years) a comparison of proportions protected with previous seroprevalence studies carried out in 2009 and 1996 for diphtheria and 1996-99, 2002-4, 2009 and 2014 for Men C. This will be done by using all the samples and calculating prevalence within individual age bands with 95% confidence intervals and inferring differences based on non-overlapping 95% CIs which is conservative to allow for multiple testing when assessing many age bands.
- For all participants, a repeat cross-sectional analysis of the geometric mean titres (with 95% CI) of antibodies against SARS-CoV-2, and proportion (with 95% CI) of participants with anti SARS-CoV-2 antibodies above a (yet to be determined) threshold of 'positivity' throughout the study period
- For participants providing multiple serum samples, analysis of the proportion of participants who were initially seronegative who subsequently developed antibodies against SARS -CoV-2
- For participants providing multiple serum samples, analysis of the kinetics of the rise and fall of antibodies against SARS -CoV-2
- Calculation of the sensitivity and specificity of salivary antibody testing compared to serum.

Exploratory analyses

- Whether ethnicity, household income or other factors collected on the questionnaire are associated with antibodies against diphtheria and / or Men C and/or SARS-CoV-2. This will be done by multivariable logistic regression.
- Comparisons between groups 1 and 2 will be performed as detailed in study statistical analysis plan in terms of:
 - representativeness of ethnicity, community identity, migrant population and socioeconomic background of local communities
 - immunological end-points

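### The comparison with earlier diphtheria and MenC surveys is not made by sample source, so a difference between survey and residual sera can be flagged as a change over time

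*Protocol*

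**What the plan says.** Among the secondary analyses, Protocol section 11.1 plans a comparison across ages 0 to 24 with "previous seroprevalence studies carried out in 2009 and 1996 for diphtheria and 1996-99, 2002-4, 2009 and 2014 for Men C". The method is fixed in the same bullet: "This will be done by using all the samples and calculating prevalence within individual age bands with 95% confidence intervals", then "inferring differences based on non-overlapping 95% CIs which is conservative to allow for multiple testing". It contains no adjustment or caveat for how the sera were obtained.

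The earlier surveys are introduced in section 5 under a heading on residual sera, which opens by saying that "PHE has been utilising residual serum samples from participating laboratories across the country". For diphtheria 2009 the source is explicit: "In this study, 150 residual sera were tested in each age group". The MenC surveys follow in the same text. The 1996 diphtheria survey is not described there.

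Section 5 then lists the weaknesses of residual sera, the first being "Samples may not be representative of the whole population". It adds: "Previous review of the source of these samples have shown considerable variation by age e.g. paediatric samples from immunocompromised children". The second primary outcome (sections 6 and 11.1) compares protection in residual and prospectively collected sera. Section 7.8 provides the contemporaneous residual sera: "It is envisaged that a similar sample size will be collected in 2019/20, and that testing of the residual sera can take place in 2021".

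**The concern.** The study exists partly because residual and actively collected sera may give different answers. The bullet on change over time nevertheless sets current estimates against residual-sera surveys without separating the two sources. If the current estimate comes from the prospective survey, or from survey and residual sera pooled, a step since 2009 or 2014 mixes a change in protection with a change in sampling frame. The non-overlap rule is described as conservative, but that guards against chance findings in many age bands, not against a systematic shift common to them. A like-for-like comparator, current residual sera tested for the same antigens, is already planned for the primary outcome but is not assigned to this analysis.

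**Working it through.** **Inputs from the protocol**
- 100 prospective sera per age band, 2300 in total, hence 2300/100 = 23 bands (section 11.2.1, Table 2).
- 150 residual sera per age group in diphtheria 2009 (section 5, Box 1).
- 3290 residual sera at ages 0 to 24 in 2017, with a similar number expected in 2019/20 (section 7.8).
- Detectable survey-versus-residual differences from 50%: 10.7 points under 4 years, 5.7 at 14 to 24, 3.9 at all ages (Table 4).

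**Assumed.** The survey-minus-residual difference *d* has no value in the protocol. Table 4 values are used only as illustrations. The historical surveys are given 150 sera in every band, a true prevalence of 50% and no real change since.

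**The protocol's own figures reproduce**
- Table 2: exact (Clopper-Pearson) intervals with n = 100 match all nine rows, for example 39.8 to 60.2 at 50%.
- Box 1: 1.96 × √(0.25/150) = 8.0 points, as stated.
- Table 4, all ages: 2300 against 3290 sera at 80% power gives 3.8 points, against 3.9 printed.

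**How much of *d* enters the comparison**
- Survey alone: all of it.
- Pooled, all ages: the survey share is 2300/(2300 + 3290) = 41%. With *d* = 3.9 the apparent change is 0.41 × 3.9 = 1.6 points.
- Pooled, under 4 years: residual sera are scarcer here. Solving Table 4's 10.7 points for the residual number, with 4 × 100 = 400 survey sera, gives about 293. The survey share is 400/(400 + 293) = 58%, so *d* = 10.7 gives 0.58 × 10.7 = 6.2 points.

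**How often the rule flags a band when nothing has changed.** Summing binomial probabilities over all outcomes in which two exact 95% intervals do not overlap (100 sera at 50% + *d* against 150 at 50%):

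| *d* (points) | Flag, one band |
|---|---|
| 0 | 0.4% |
| 3.9 | 1.2% |
| 5.7 | 2.3% |
| 10.7 | 11.2% |

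Over the four single-year bands under 4, to which 10.7 relates, the chance of at least one flag is 1 − (1 − 0.112)⁴ = 38%, taking bands as independent. With *d* = 0 it is 1 − (1 − 0.0041)⁴ = 1.6%. Pooled, with 100 + 73 = 173 sera per band and an apparent change of 6.2 points, one band is flagged 3.9% of the time and at least one of four 15%.

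**The like-for-like comparison**
- On average there are 3290/23 = 143 current residual sera per band. Against 150 historical sera with no true change, the flag rate is 0.4%. A source effect common to both surveys cancels.
- For a true 20-point change the rule detects it in 74% of cases with 143 residual sera, against 61% with 100 survey sera.
- Under 4 years there are about 293/4 = 73 residual sera per single-year band. Detection falls to 50%, and the half-width near 50% is 1.96 × √(0.25/73) = 11.5 points, against 9.8 with 100 sera.

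**The case against.** The wording does not mention pooling. The two bullets before it are limited to prospective sera with known vaccination history, so the broader term may only lift that limit, or may mean that both sources are used and shown separately, which would include the like-for-like comparison. A detailed analysis plan is promised. This stands as far as it goes: the term is undefined. But the bullet already fixes comparators, estimator and decision rule, and two natural readings are not like-for-like, so the protocol should settle it.

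The primary analysis will estimate the survey-versus-residual difference, so a careful author could interpret the comparison correctly. That is true, but nothing ties the two results together.

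The remedy is also not free of assumptions. Section 5 says that residual numbers in children are generally low and unlikely to support single-year bands by region, and nothing shows that the make-up of residual samples has stayed stable since 1996. Both limits stand and shape the fix.

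A reader might infer three stronger things that the documents do not support. First, that all the comparators are known to be residual sera: this is explicit only for diphtheria 2009. Second, that the bias is 3.9 to 10.7 points: these are differences detectable with 80% power, not estimates of bias. Third, that the protocol attributes differences to waning or vaccine policy: this bullet speaks only of inferring differences in the proportions protected.

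**Conclusion.** The concern holds in limited form. Section 11.1 does not separate sources in the comparison with earlier surveys. On the survey-only and pooled readings, a difference that the study itself sets out to test can be flagged as a change over time. The size is unknown. If the difference were as large as Table 4's detectable limits, it would enter in full on the survey-only reading (3.9 points at all ages, 10.7 under 4 years) and in part if pooled (about 1.6 and 6.2 points). Per-band false flags would rise from 0.4% to between 1.2% and 11.2% on the survey-only reading. These rates assume a 50% baseline, 150 historical sera per band and no true change. This is a secondary analysis, and the problem is worth correcting because the sera that resolve it are already to be tested. It does not make the comparison invalid as such: if the primary analysis shows little difference between sources, little is at stake.

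**What to change.** In the historical-comparison bullet of section 11.1:

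- Replace the undefined sample term with estimates calculated separately for prospective and current residual sera, not pooled.
- Name current residual sera versus the historical residual surveys as the like-for-like time comparison, with broader age bands where residual numbers are small (under 4 years).
- State the sample source of each historical survey, including diphtheria 1996.
- Show the prospective estimates beside this comparison, and interpret any survey-versus-history difference against the contemporaneous survey-versus-residual difference from the primary analysis.
- State as a limitation that the comparison assumes a stable make-up of residual samples over time.

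The cost is a few sentences. No further samples or assays are needed, because the residual sera must be tested for diphtheria and MenC for the primary outcome. The price is wider intervals or coarser bands in the youngest ages.

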	 To determine the prevalence of SARS-CoV-2 infections in 0 – 24 year olds, and variation in prevalence in time, age, ethnicity and geography (cross-sectional sero- epidemiological study) 	 Serum IgG to SARS-CoV-2 antigens, including spike protein and/or nucleocapsid (as measured by ELISA and/or neutralising assay)
	 To determine the kinetics of antibodies specific to SARS- CoV-2 following infection in a paediatric population (serial blood sampling in population sub-group) To determine relationship between serum and salivary antibodies against SARS-CoV-2 	 Serum IgG to SARS-CoV-2 antigens, including spike protein and/or nucleocapsid (as measured by ELISA and/or neutralising assay) Salivary IgG to SARS-CoV-2 antigens, including spike protein and/or nucleocapsid (as measured by ELISA)
Exploratory	 Comparison between recruitment strategies between groups The presence of SARS-CoV-2 virus in saliva in a sub-set of study participants 	 Representativeness of participants sampled, in terms of the local population's ethnicity, community identity, migrant population and socioeconomic background Differences in immunological read outs
	 To characterise T cell responses against SARS-CoV-2 in antibody seropositive and seronegative participants. 	 PCR for SARS-CoV-2 on saliva samples stored and processed at the end of the study.

 Humoral and cellular immunity against non SARS- CoV-2 coronaviruses 	 T cell responses to SARS-CoV-2 antigens including, but not limited to S, M and N proteins, as measured by techniques including, but not limited to ELISpot ICS Proliferation assay
	 Antigen specific IgG and T cells against non-SARS-CoV-2 coronaviruses (e.g. NL62 and 229E)

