6. OBJECTIVES AND OUTCOME MEASURES

	Objectives	Outcome Measures
Primary	 To evaluate the feasibility and added public health benefit of an England, population based sero - epidemiological programme in 0 to 24 year olds 	 Representativeness of participants sampled, in terms of the local population's ethnicity, community identity, migrant population and socioeconomic background Comparison with serological markers of immunity for vaccine preventable diseases as measured in an age matched cohort in current residual sera programme
Secondary	 To evaluate the effectiveness of recruitment methods employed To assess, in relevant age groups, antibody concentrations against infections and vaccine preventable diseases including, but not limited to diphtheria, group C meningococcus and novel coronavirus (COVID-19) 	 Recruitment rate per month, recruitment rates as percentage of potential participants contacted, cost per sample obtained disease specific correlates of protection/markers of immunity, e.g. : Anti-Diphtheria Toxoid IgG concentrations Capsular Group C meningococcal Serum bactericidal activity (SBA) titres Serum IgG to SARS-CoV-2 antigens, including spike protein and/or nucleocapsid (as measured by ELISA and/or neutralising assay)
	• To develop a store of sera from a representative section of 0 to 24 year olds available for future testing of immunity against other infectious diseases of relevance to UK immunisation schedule and public health.	• A collection of anonymised sera from participants with appropriate consent and known demographic details and immunisation history'
	 To determine the prevalence of SARS- CoV-2 infections in 0 – 24 year olds, and variation in prevalence in time, age, ethnicity and geography (cross- sectional sero-epidemiological study) 	 Serum IgG to SARS-CoV-2 antigens, including spike protein and/ or nucleocapsid (as measured by ELISA and/or neutralising assay)

	 To determine the kinetics of antibodies specific to SARS-CoV-2 following infection in a paediatric population (serial blood sampling in population sub-group) To determine relationship between serum and salivary antibodies against SARS-CoV-2 	 Serum IgG to SARS-CoV-2 antigens, including spike protein and/or nucleocapsid (as measured by ELISA and/or neutralising assay) Salivary IgG to SARS-CoV-2 antigens, including spike protein and/or nucleocapsid (as measured by ELISA)

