8.2. Inclusion Criteria

Participants MUST FULFILL each of the below criterion:

- Parents/legal guardians or adult participant* is willing and able to give informed consent for participation in the study.
- Male or Female, aged 0 24 years inclusive (Group 1) and 0 19 inclusive (Group 2 and 3).
- Parents/legal guardians or adult participants are willing to allow their General Practitioner or relevant NHS databases to be contacted for a full immunisation history

* For the purposes of this study an adult will be defined as all those 16 years of age or over.

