9.6.2 Subsequent visits (longitudinal sampling cohort)

A subset of participants, distributed equally across 0-19 age groups, will be recruited into a longitudinal sampling sub-study.

If the participant provides consent for subsequent visits, then up to 3 additional visits will be undertaken with a minimum 2 months between visits. These visits will be conducted as for Visit 1, except that the questionnaire will be limited to COVID-19 symptoms in the participant or household members and a sample of saliva will be collected by the participant or their parents/legal guardians, as per the Clinical Study Plan.

Sites undertaking PBMC processing in the longitudinal cohort will select individuals where a whole blood sample will be taken. Total blood volume will remain the same, with whole blood subsequently separated into plasma and PBMC's.

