		significance, assuming		significance, assuming	
		population much larger		population much larger	
		than sample (>=10 fold))		than sample (>=10 fold))	
5%	3.0-7.7	2.3,9.1	4.1-6.0	3.8,6.5	
10%	7.2-13.5	6.0,15.3	8.8-11.3	8.2,12.0	
15%	11.6-19.0	10.0,21.0	13.6-16.5	12.9,17.3	
20%	16.1-24.4	14.3,26.6	18.4-21.7	17.6,22.5	
25%	20.7-29.7	18.8,32.0	23.2-26.8	22.4,27.7	
30%	25.5-34.9	23.3,37.3	28.1-31.9	27.2,32.9	

Table 3: Assessment of representativeness, precision and detectable differences

Comparison with residual samples

For comparison with the residual samples this is considered within age strata and is based on the 2017 data on residual samples for the numbers of residual strata by age. Due to the smaller number of residual samples in younger age groups (one of the key reasons for undertaking a community based seroprevelance survey), detectable differences are relatively large in those <4 years. In older age groups relatively, small differences can be detected in >4 year age bands. The example given below is for when the observed prevalence is 50% is the survey which is conservative as this gives the largest detectable differences.

Table 4: Comparison to residual samples by age strata with a total sample size of 2300

Age	Detectable difference from 50% (80% power, 5% significance)
<4	10.7
4 to 8	8.7
9 to 13	8.1
14 to 24	5.7
All Age	3.9

11.2.2: Group 1 and 2 combined

Sample size for SARS-COV-2 incidence based on change in prevalence

Across group 1 and 2 combined there will be over 3500 blood samples from 2800 to 3500 participants in total, at least 3200 of which will be from participants 19 years of age or younger. The intent of this is to obtain blood samples across 4 age bands (i.e. 100 in each of 0 -4 years, 5-9 years, 10-14 years, 15-19 years)to the end of the study. This will include sample taken from the longitudinal cohort, with seroprevalence calculations taking into account over-sampling of participants with positive SARS-Cov 2 antibodies at V1.

The table below shows the precision (95% CI) of estimates of change in prevalence (incidence) with 100 samples at each of two time points. For example with a prevalence of 10% at baseline and 30% at the next time point the incidence is 20% with 95% CI 9.3-30.7. The aim is to achieve 100 in each of 4 age groups at each time point.

Prevalence				
At next time				11.3. Analysis
point	0%	10%	20%	populations
10%	10 (4.1, 15.9)			 The analysis population for recruitment rates will be all

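### Serum IgG in infants enrolled from birth is counted as their own SARS-CoV-2 infection, so maternal antibody biases the youngest age band upward and can enter the post-infection kinetics

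*Protocol*

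**What the plan says.** Section 8.2 sets no minimum age above 0 in any group, and Table 1 in Section 9.6.1 has separate blood-volume rows for infants under 2 months, 2-6 months and 6-12 months. Young infants are therefore meant to be bled.

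The Synopsis states the objective as "To determine the prevalence of SARS-CoV-2 infections in 0 – 24 year olds, and variation in prevalence in time, age, ethnicity and geography", with serum IgG to spike and/or nucleocapsid as its outcome. Section 5 describes seropositivity "as a marker of infection with this novel coronavirus". Section 11.1 then plans, for all participants, the "proportion (with 95% CI) of participants with anti SARS-CoV-2 antibodies above a (yet to be determined) threshold" of positivity through the study period. Section 11.3 defines the seroprevalence population as everyone with a sample and a laboratory result. In Section 11.2.2 the youngest SARS-CoV-2 band is 0-4 years, with 100 samples per time point, and a change in prevalence is read as incidence.

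For serial samples, the Section 6 objective is antibody kinetics "following infection in a paediatric population". The cohort in Section 9.6.2 is "A subset of participants, distributed equally across 0-19 age groups". Section 11.2.2 says that seroprevalence calculations will take into account "over-sampling of participants with positive SARS-Cov 2 antibodies at V1". Section 11.1 analyses the rise and fall of antibody in participants with multiple sera.

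The protocol nowhere mentions maternal or passively acquired antibody. Personal and household coronavirus history is collected (Section 7.6), but it is not linked to this question.

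**The concern.** IgG is the antibody class that passes from mother to fetus. In the first months of life a positive result can therefore show the mother's antibody and not an infection in the infant. Choosing between spike and nucleocapsid does not settle this, because maternal IgG after infection can be directed at either.

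Two stated objectives are affected. The comparison of infection prevalence by age is biased upward at its youngest end, and the bias follows adult seroprevalence, so it can change between time points with no change in infant infection. In the kinetics analysis, the loss of passively acquired IgG is not antibody behaviour after infection, yet an infant positive at the first visit can be followed as if it were. Over-sampling of first-visit seropositives makes such follow-up more likely.

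**Working it through.** **The plan's own figure.** Table 5 gives a change from 10% to 30%, with 100 samples at each time, as 20% (9.3-30.7). The standard error is √(0.10×0.90/100 + 0.30×0.70/100) = √0.0030 = 0.0548, and 1.96 × 0.0548 = 0.107, so the interval is 9.3% to 30.7%. It reproduces and is not in dispute.

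**Inputs.**
- True infection prevalence p = 4%. This is the Section 11.4 figure for the white community, used here only as a working level.
- Share of the 0-4 band carrying the problem, f. Group 1 has 100 per one-year band, so under-1s are 100/500 = 20% and, with even ages, under-6-month infants are 10%. Group 2 is balanced only by five-year band, so its share is not fixed.
- Maternal seroprevalence m = 5%, 10% or 15%. Assumed; the protocol gives none.
- Persistence: every infant of a seropositive mother is taken to be positive up to 6 months (f = 0.10) or 12 months (f = 0.20). Assumed.
- Infant infection is taken as independent of the mother's status. Assumed.

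**Excess in the 0-4 band** = f × m × (1 − p).

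| Persistence | m = 5% | m = 10% | m = 15% |
|---|---|---|---|
| 6 months | 0.10×0.05×0.96 = 0.48 points | 0.96 | 1.44 |
| relative to 4% | 12% | 24% | 36% |
| 12 months | 0.96 points | 1.92 | 2.88 |
| relative to 4% | 24% | 48% | 72% |

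The exact 95% interval for 4/100 is 1.1-9.9%.

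**Group 1's age-0 band (100 infants).** With 6-month persistence half the band is exposed, so maternal positives number 100 × 0.5 × m × 0.96 = 2.4, 4.8 or 7.2, against 4 from own infection. With 12-month persistence they number 4.8, 9.6 or 14.4. Maternal positives outnumber own positives when m exceeds 0.04/(0.5×0.96) = 8.3% (6 months) or 0.04/0.96 = 4.2% (12 months).

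**Time trend.** If m rises from 5% to 15% while infant infection stays constant, the 0-4 band shows a spurious rise of 1.44 − 0.48 = 0.96 points (6 months) or 2.88 − 0.96 = 1.92 points (12 months). Table 5 half-widths run from 5.9 points (0% to 10%) to 12.6 points (20% to 50%).

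**Kinetics.** With ages even over 0-19, under-1s are 1/20 = 5% of the cohort and under-6-month infants 2.5%. At m = 10% and p = 4%, maternal positives are 0.025×0.10×0.96 = 0.0024, or 0.0024/0.0424 = 6% of seropositives (6 months), and 0.0048/0.0448 = 11% (12 months). Within the 0-4 band the shares are 0.0096/0.0496 = 19% and 0.0192/0.0592 = 32%.

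**The case against.** The strongest reply is that the Section 11.1 sentence, read alone, reports antibody prevalence and is correct, and that infant handling belongs in the statistical analysis plan. The first half is true of that sentence. But the objective it serves is infection prevalence, Section 5 reads seropositivity as infection, and the protocol itself fixes the all-participants rule and the analysis population. An infant exclusion made only in the analysis plan would depart from those statements.

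It is also fair that infants need not disappear into the 0-4 band. Group 1 has its own age-0 band, and Section 11.2.1 takes one-year bands as usual. Separate display is possible under the design, but a separate age-0 figure still labelled infection is more biased than the pooled one.

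The formula has no term for incomplete transfer or gradual decay, so for a given m and persistence it sits near a ceiling. The youngest infants may also be under-represented, since samples below the minimum volume are failed enrolments and Table 1 caps those under 2 months at 2 ml. Both points stand.

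Three stronger readings are not supported:
- That most age-0 positives would be maternal. This fails at 5% maternal seroprevalence with 6-month persistence (2.4 maternal against 4 own).
- That the study would report faster waning in young children. Section 11.1 plans the rise and fall of antibody and states no age comparison of kinetics.
- That the time trend is seriously distorted. The spurious change of about 1-2 points is small beside the Table 5 half-widths.

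**Conclusion.** The concern holds as a bias built into a stated rule. Followed as written, the protocol counts transplacental IgG as the infant's own infection and allows its decay into an analysis of kinetics after infection. The direction is firm. The size is not, because neither maternal seroprevalence nor persistence is given. With a true 4%, even ages, maternal seroprevalence of 5-15% and full persistence, the 0-4 estimate rises by about 0.5-1.4 points (6 months) or 1.0-2.9 points (12 months).

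At 100 samples per band this will often lie within sampling error. Unlike sampling error, it does not shrink as samples are pooled, it grows with adult seroprevalence, and it is larger in Group 1's age-0 band. Only secondary objectives are affected; the primary outcomes on representativeness and on comparison with residual sera for vaccine-preventable diseases are not.

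**What to change.** Change the analysis text in Sections 11.1 and 11.2.2:

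1. Pre-specify an age below which infants are reported separately as antibody prevalence, not infection.
2. Estimate infection prevalence for the youngest band from that age upward, for example from 6 months with a sensitivity analysis from 12 months, and label the age range accordingly. The protocol supplies no basis for a cut-off, so the choice needs a stated justification.
3. Exclude from the main post-infection kinetics analysis every participant who was seropositive at the first visit below the same age, whatever their later IgG course, and describe them separately.

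Keeping such infants when IgG later rises should be avoided: it selects on the outcome, retaining risers and dropping truly infected infants whose antibody falls. Changing who counts towards the seropositive over-sample is no longer practical, since protocol V9.0 is dated 28 June 2021 and recruitment was planned to end that month.

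The cost is small. Age is already recorded, and Table 1 requires it to within months in infancy. The infection estimate loses about 10% of the 0-4 samples (about 20% in the 12-month sensitivity analysis). At the same prevalence, intervals widen by √(100/90) = 1.05, about 5%, or √(100/80) = 1.12, about 12%. Some truly infected infants are left out of the main kinetics analysis.
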